
11.0 Data Analysis and Data Management

Data Analytic Plan for Aim 1 Qualitative Data

Qualitative data from interviews, quantitative data from questionnaires, and video and audio recordings will be incorporated for mixed methods data analysis⁶⁶. This approach was chosen because, while quantitative data can identify usability errors and areas of dissatisfaction, qualitative data provides guidance on the root of errors and methods for optimization. Qualitative data will be analyzed using NVivo software⁶⁷ and a deductive/inductive template analysis approach^{68,69} using iterative codes to identify core concepts⁷⁰. From these core concepts, we will determine the needs, concerns, and impressions of our prototypes. Two coders will independently review and code data using an iterative, team-based process with discrepancies resolved by the study team. Qualitative themes will be supplemented by patterns identified in quantitative results. After completing qualitative and quantitative data analysis independently, data from each source will be synthesized using graphical matrix configurations for data triangulation⁷¹. This analytic approach was selected due to the expectation that participants will raise unanticipated needs. Mean ratings of VapeX components from the After-Scenario Questionnaires (ASQs) will be calculated and components with lowest satisfaction will be flagged for refinement. Video and audio recordings be coded for navigation errors (difficulty locating a function), content errors (difficulty due to information labeling), and usage errors (improper tool use). Problems will be grouped according to severity (critical/serious/minor).

Sample Size Estimation

As a pilot, our goal is to determine VapeX feasibility/acceptability and estimate effect sizes for a larger Phase II project. We can obtain more robust estimates in the VapeX group via 1:1 randomization with the first 5 being assigned to the VapeX group for usability testing. Toward these ends, we will randomize **49 to VapeX and 49 to TAU**. To account for 20% attrition, we will enroll a maximum of 108 participants.

Data Analytic Plan for Aim 2

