Depression. Similar generalized linear mixed models will be used to examine group differences (VapeX vs. TAU) in depression (BDI-II) over time along with an interaction between group and time adjusting for baseline differences and baseline depression. All models will include a random component to account for any clustering effects from the clinic from which the participant was recruited along with a random effect for repeated measures within an individual. Sex will be examined for inclusion as a covariate in all models. These generalized linear models allow for examination of overall main effects of group, time, and the interaction between group and time, while also accounting for repeated measures within participants and clustering with clinics^{72,73}.

Missing Data. All randomized participants will be included in primary analyses, and imputation methods will be used to accommodate missing data if missing data is >10%. Sensitivity analyses will be done using only those with complete data, with results compared to primary analyses. Attrition will be assessed to determine whether there is differential dropout by group.

Adverse Events (AEs). AEs will be defined as a clinically significant (i.e., 10-point⁶⁴) increase in depression on the BDI-II from baseline or any incidence of suicidality (response of "I would like to kill myself" or "I would kill myself if I had the chance" on the BDI-II suicidality item). We will determine the incidence of AEs and associated 95% CIs. A chi-square test will determine if the rate of AEs is greater than 5% in any group.

Data Management

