Accuracy and completeness of the data collected will be ensured by weekly review. The REDCap system does not accept outliers, illogical response patterns, etc. The PI and research assistant will have weekly meetings to discuss any qualitative comments received during data collection and any problems in data collection. The PI will examine the database for potential irregularities monthly. Initial data analyses will examine distributions of variable scores and comparability of baseline characteristics across conditions (for Aim 2) in case analyses need to be adjusted for these. Confidentiality procedures are outlined above.

Regulatory Issues

This study will be registered on ClinicalTrials.gov. The study does not require an Investigational Device Exemption (IDE) from the FDA. All serious AEs will be reported to the MUSC Committee on Human Research within 48-hours. Follow-up of all unexpected and serious AEs will also be reported. All AEs will be reviewed weekly by the PI and yearly by the IRB. Any significant actions taken by the local IRB and protocol changes will be relayed to the funding agency. We estimate the significant AE rate to be very low (<5%). If monthly monitoring indicates the rate is above this, we will convene a meeting of the DSMB. Potential conflicts of interest (COI) will be reported using the rules of MUSC's COI committee.

Trial Safety

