13.0 Risks to Subjects

The potential risks in this study include those related to: a) depressive symptoms, b) clinical deterioration, c) confidentiality, d) potential data breach from the app database, and e) frustration. Risk mitigation strategies are outlined below and have previously been implemented with success in [name] prior trials.

a) Depressive symptoms: Depressive symptoms will be monitored via the BDI-II. All participants will complete the BDI-II weekly online via a REDCap survey that is accessible via mobile phone web browsers. All participants will own smartphones. Thus, all participants should have access to the online BDI-II assessments.

b) Clinical deterioration: [name] and her research team will monitor participant BDI-II scores for possible clinical deterioration (i.e., increasing depressive symptoms and/or the development of suicidal ideation) throughout the course of the study as participants complete the BDI-II weekly. Clinical deterioration will be defined as an increase of 10 or more points on the BDI-II from the baseline BDI-II assessment or a response of "I would like to kill myself" or "I would kill myself if I had the chance" on the suicidal thoughts or wishes item of the BDI-II. Our team has developed real-time alerts within REDCap which alert the investigative team if a participant completes a BDI-II assessment and evidences clinical deterioration. In the event that a participant evidences clinical deterioration, [name] will contact the participant via phone and will provide referrals for local mental health resources for depression treatment. [name] will suggest that the participant seek treatment and then will follow-up with the participant via phone one week later. If the participant is under the age of 18, this discussion will occur both with the participant and with the parent/legal guardian. If [name] is unavailable, Drs. [name], [name], and/or [name], all licensed clinicians, will serve as clinical back-ups.

In the event that a participant reports suicidal ideation either during study screening or during subsequent assessments, [name] (or back-up clinician) will 1) page the participant's attending primary care provider (if the participant is an MUSC patient) and 2) complete a risk assessment with the participant via phone. If the participant is under the age of 18, the participant's parent/legal guardian will also be part of this discussion. [name] will query the participant for details regarding the suicidal

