Protection against risk resulting from depressive symptoms includes the following: Regarding suicidal ideation and broader mental health concerns, [name] (or back-up clinician), a licensed clinical psychologist, will take appropriate action as outlined by the MUSC IRB, NIH, and the State of South Carolina, which may include paging the participant's referring physician, disclosing information to the participant's parent/legal guardian, contacting the authorities and/or pursuing involuntary commitment at a mental health facility. If participants present no imminent danger but also need more extensive treatment of mental health concerns, they (and their parent/legal guardian, as appropriate) will be given appropriate referrals. As noted above, BDI-II data will be monitored over time in order to detect any possible clinical deterioration. BDI-II data will be monitored using only the participants' subject numbers. Should a participant evidence clinical deterioration, [name] will then use the participant database in order to obtain contact information for the participant based on their subject number. We will also form a Data Safety and Monitoring Board (DSMB) comprised of individuals with expertise in adolescent depression and substance use treatment, primary care, and clinical trials, as well as a statistician. If the percent of serious or severe AEs related to clinical deterioration appears to be greater than 5% the DSMB will be notified to make a decision on early termination of the study.

Regarding recordings, all focus group sessions will be audio recorded and transcribed with recordings stored on an MUSC secure, password protected server. Recordings will be destroyed within one year of recording. Only IRB approved research staff will have access to recordings. Recordings will be destroyed within 12 months of completion of the entire study. Only IRB approved research staff will have access to recordings.

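### Adverse-event incidence is tested in each group only against a fixed 5%, with no VapeX-versus-TAU comparison, and the chi-square test suits 49 per arm poorly

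*Combined protocol and SAP*

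**What the plan says.** Section 11.0, Adverse Events, gives the definition: "AEs will be defined as a clinically significant (i.e., 10-point⁶⁴) increase in depression on the BDI-II from baseline or any incidence of suicidality". Section 13.0 uses the same threshold for clinical deterioration, worded as "an increase of 10 or more points on the BDI-II from the baseline BDI-II assessment". The BDI-II is completed at baseline and at Weeks 1 to 4, so each participant has four occasions to meet the definition.

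The analysis is two sentences in section 11.0: "We will determine the incidence of AEs and associated 95% CIs", followed by "A chi-square test will determine if the rate of AEs is greater than 5% in any group". The plan gives no significance level, sidedness or interval method, and does not say where 5% comes from.

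Two monitoring rules use the same number. Section 12.0, Regulatory Issues, expects a significant-AE rate below 5% and adds "If monthly monitoring indicates the rate is above this, we will convene a meeting of the DSMB". Section 13.0 says "If the percent of serious or severe AEs related to clinical deterioration appears to be greater than 5% the DSMB will be notified", with early termination as the decision to be taken. Neither rule refers to a difference between arms.

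The sample-size text randomizes "49 to VapeX and 49 to TAU". Five further participants are assigned to VapeX without randomization, for usability testing.

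**The concern.** The trial has a concurrent randomized control. For safety, its main use is to show how often a 10-point BDI-II rise or a suicidality response occurs without the app. The AE analysis does not use it. Each group is compared with an external 5% that is not tied to any background rate. If VapeX exceeds 5%, the test cannot say whether the app or the population is responsible. If neither arm exceeds it, the result may be taken as reassurance that 49 participants per arm cannot give.

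This also leaves a gap against the pilot's stated purpose, which includes estimating effect sizes for a larger study. A between-arm estimate of deterioration is one such effect size, and it needs no extra data.

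**Working it through.** **Plan's own figure.** The 5% is asserted, not derived, so there is nothing to reproduce. What can be computed is how the test behaves.

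**Inputs from the documents.** n = 49 per arm; benchmark 5%; four post-baseline BDI-II assessments. **Assumed:** significance level 0.05, and every randomized participant counted once, as having at least one AE or none.

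**1. Adequacy of chi-square.** The expected count at 5% is 49 × 0.05 = 2.45, below the usual minimum of 5.

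**2. When an arm is flagged.** z = (k/49 − 0.05) / √(0.05 × 0.95 / 49).

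| Events k | Rate | z | z² | One-sided p | Two-sided p | Exact P(X ≥ k) at 5% |
|---|---|---|---|---|---|---|
| 5 | 10.2% | 1.67 | 2.79 | 0.047 | 0.095 | 0.097 |
| 6 | 12.2% | 2.33 | 5.41 | 0.010 | 0.020 | 0.035 |

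One-sided chi-square flags at 5 events, with actual size 9.7%. Two-sided chi-square (critical value 3.84) and the one-sided exact test flag at 6, with actual size 3.5%. The plan's wording is directional but does not settle which applies.

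**3. Chance of flagging a true excess,** from the binomial with n = 49:

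| True rate | Flag at ≥ 5 | Flag at ≥ 6 |
|---|---|---|
| 10% | 55% | 37% |
| 15% | 88% | 76% |

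**4. What a non-significant result can show.** With 0 events of 49, the exact (Clopper-Pearson) two-sided 95% upper limit is 1 − 0.025^(1/49) = 7.3%. Even the one-sided 95% limit is 1 − 0.05^(1/49) = 5.9%. No possible result in one arm excludes rates above 5%.

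**5. What the between-arm estimate adds.** Newcombe 95% CIs for VapeX minus TAU:

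| VapeX | TAU | Result of the 5% test | Difference (95% CI) |
|---|---|---|---|
| 8/49 | 8/49 | both arms flagged | 0 (−14.9 to 14.9) points |
| 14/49 | 6/49 | both arms flagged | +16.3 (0.2 to 31.6) points |
| 5/49 | 0/49 | VapeX flagged one-sided; no arm flagged two-sided or exact | +10.2 (0.9 to 21.8) points |

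The first two rows get the same answer from the planned test, although one shows no difference and the other a substantial one.

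Check of the third row: the Wilson limits are 4.4% to 21.8% for 5/49 and 0% to 7.3% for 0/49. The lower limit is 10.2 − √((10.2 − 4.4)² + (7.3 − 0)²) = 10.2 − 9.3 = 0.9. The upper limit is 10.2 + √((21.8 − 10.2)² + 0²) = 21.8.

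**6. Detection if the between-arm interval were used as a test.** Chance that the Newcombe lower limit exceeds zero, by exact enumeration, against the chance that the 5% check flags VapeX at ≥ 6:

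| True VapeX vs TAU | Newcombe CI above zero | 5% check flags VapeX |
|---|---|---|
| 10% vs 5% | 11% | 37% |
| 10% vs 2% | 30% | 37% |
| 15% vs 5% | 33% | 76% |

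**7. Background fluctuation (illustration only).** The documents give neither a BDI-II SD nor a retest correlation r. Assume normal scores, equal correlation across assessments, no mean change and SD 10. The SD of a change from baseline is 10 × √(2(1 − r)): 4.5, 6.3 and 7.7 at r = 0.9, 0.8 and 0.7. Simulation (400,000 draws) gives the chance of a rise of at least 10 in one or more of four weeks:

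| r | Participants with a rise ≥ 10 | Both arms flagged (≥ 6 of 49 each) |
|---|---|---|
| 0.9 | 4% | about 0% |
| 0.8 | 16% | 67% |
| 0.7 | 26% | 99% |

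At r = 0.8, a 3-point mean improvement by Week 4 lowers these to 10% and 11%. With SD 8, r = 0.8 and no mean change, they are 7.5% and 3%.

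**The case against.** The 5% figure is an absolute benchmark, also used for monitoring. If both arms of depressed adolescents exceed it, the DSMB would want to know whatever the cause. An absolute question is legitimate, and at this size the check has more power than a between-arm test when TAU is near 5% (step 6). This stands, and it is why the check should be kept. A reader might infer that it should give way to the between-arm comparison; the numbers do not support that.

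The plan also has partial cover: incidence with confidence intervals, a between-arm mixed model of BDI-II scores, case-by-case judgement of relation to app use, and DSMB review. These lower the stakes but leave the gap open. The incidence sentence does not name a between-arm difference. The mixed model compares mean scores, not the proportion with large deterioration or a suicidality response. The case judgement has no comparator, and no arm contrast is specified for the DSMB.

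Two stronger readings are tempting. One is that the rule lets 5/49 against 0/49 pass unflagged. That holds only for a two-sided or exact test; a one-sided chi-square, which the directional wording allows, flags VapeX at p = 0.047. The other is that ordinary symptom fluctuation will flag both arms. That rests on BDI-II variability which the documents do not give: at SD 10 and r = 0.9 the background rate is 4%, below the benchmark.

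**Conclusion.** The concern holds in limited form. It is a textual fact that AE incidence is tested only against 5% within each group and that no section plans a VapeX-versus-TAU comparison of it. The AE analysis therefore cannot attribute an excess to the app, although a randomized comparator is available.

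That the test is indeterminate and approximate follows from the plan's own 49 per arm, given a 0.05 level. The boundary is 5 or 6 events depending on an unstated choice, actual size is 9.7% or 3.5%, and a true 10% rate is flagged 55% or 37% of the time. A non-significant result cannot establish a rate of 5% or less.

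Whether both arms would be flagged without any app effect stays open: the answer runs from about 0% to 99% over r = 0.9 to 0.7 at an assumed SD of 10. The point is worth correcting before analysis. It does not undermine the trial's main outcomes.

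**What to change.** In section 11.0, Adverse Events:

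- Keep 5% as an absolute benchmark, but test it with a one-sided exact binomial test at a stated level. Report each arm's proportion of participants with at least one AE with an exact (Clopper-Pearson) 95% CI.
- Interpret a non-significant result by quoting the upper confidence limit. Do not conclude from it that the rate is no higher than 5%.
- Add the VapeX minus TAU risk difference in participants with at least one AE, among the 98 randomized, with a Newcombe 95% CI. Label it an estimate, not a significance test.
- Show the five non-randomized VapeX participants separately, and say whether they enter any per-arm rate.
- Reconcile the event sets to which 5% is applied: all defined AEs in section 11.0, significant AEs in section 12.0, and serious or severe AEs related to deterioration in section 13.0.

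The cost is a few lines of SAP text and one table, with no new data and no design change. The downside is that the between-arm interval will be wide (about ±15 points at 8 events per arm) and, read as a test, would detect less than the 5% check when the TAU rate is near 5%. The plan should say so in advance.

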13.0 Risks to Subjects

The potential risks in this study include those related to: a) depressive symptoms, b) clinical deterioration, c) confidentiality, d) potential data breach from the app database, and e) frustration. Risk mitigation strategies are outlined below and have previously been implemented with success in [name] prior trials.

a) Depressive symptoms: Depressive symptoms will be monitored via the BDI-II. All participants will complete the BDI-II weekly online via a REDCap survey that is accessible via mobile phone web browsers. All participants will own smartphones. Thus, all participants should have access to the online BDI-II assessments.

b) Clinical deterioration: [name] and her research team will monitor participant BDI-II scores for possible clinical deterioration (i.e., increasing depressive symptoms and/or the development of suicidal ideation) throughout the course of the study as participants complete the BDI-II weekly. Clinical deterioration will be defined as an increase of 10 or more points on the BDI-II from the baseline BDI-II assessment or a response of "I would like to kill myself" or "I would kill myself if I had the chance" on the suicidal thoughts or wishes item of the BDI-II. Our team has developed real-time alerts within REDCap which alert the investigative team if a participant completes a BDI-II assessment and evidences clinical deterioration. In the event that a participant evidences clinical deterioration, [name] will contact the participant via phone and will provide referrals for local mental health resources for depression treatment. [name] will suggest that the participant seek treatment and then will follow-up with the participant via phone one week later. If the participant is under the age of 18, this discussion will occur both with the participant and with the parent/legal guardian. If [name] is unavailable, Drs. [name], [name], and/or [name], all licensed clinicians, will serve as clinical back-ups.

In the event that a participant reports suicidal ideation either during study screening or during subsequent assessments, [name] (or back-up clinician) will 1) page the participant's attending primary care provider (if the participant is an MUSC patient) and 2) complete a risk assessment with the participant via phone. If the participant is under the age of 18, the participant's parent/legal guardian will also be part of this discussion. [name] will query the participant for details regarding the suicidal

ideation, including a likelihood of harming oneself imminently and a plan for committing suicide. If the participant reports an imminent likelihood of harming him/herself or a plan for committing suicide, [name] will call emergency services and will remain on the phone with the participant until emergency services arrive. Contact information including home address will be collected during study screening and will be provided if necessary to emergency services personnel. [name] is a licensed clinical psychologist and has more than 10 years of experience conducting suicide risk assessments. In the event that a participant evidences clinical deterioration, the participant will be allowed to continue in the trial, but we will recruit an additional participant for data collection purposes.

c) Confidentiality: Participants will be made aware of limits to confidentiality at the beginning of screening and during informed consent which includes a report of suicidal or homicidal intent or report of abuse or neglect. If the participant is under the age of 18, they will also be notified that clinical information disclosed as part of the research study (e.g., clinical deterioration including significant increases in depressive symptoms and/or suicidality, vaping status) may be shared with their parent or legal guardian. If the participant reports suicidal or homicidal intent or abuse/neglect during screening or at any point during the trial, [name] will take appropriate action as outlined by the MUSC IRB, NIH, and the State of South Carolina, which may include paging the participant's physician, contacting the authorities and/or pursuing involuntary commitment at a mental health facility. If participants present no imminent danger but also need more extensive treatment of mental health concerns, they will be given appropriate referrals. All individual interviews will be recorded, transcribed, and destroyed within 12 months of completion of the entire study to protect confidentiality.

d) Data breach: Although health information will be collected within VapeX (e.g., daily mood ratings, activities, values, vaping), personally identifiable information will intentionally not be collected within the app (e.g., name, phone number, email address, etc.), and thus we will not collect nor will we retain protected health information (PHI). In the event of a data breach, it is important to note that health information will not be able to be tracked back to specific individual users. By refraining from collecting PHI within the mobile app, we ensure HIPPA compliance while also protecting the identities of our users. In the event of a data breach, all app users will be notified via email.

e) Frustration: Participants may become frustrated while completing questionnaires or while using VapeX. Participants will be informed that they may refuse to answer any question(s) that they do not wish to answer and that they may discontinue use of VapeX at any time.

Adequacy of Protection Against Risks

Recruitment and Informed Consent

Study participants will primarily be recruited from local primary care/family medicine clinics associated with MUSC's Primary Care Integrated Center of Clinical Excellence (ICCE). Study recruitment will occur proactively, and we will utilize cold contact procedures and available EHR data to identify ICCE patients between the ages of 16 and 20 with depressive symptoms who vape nicotine. As part of routine clinical care, all primary care patients (including adolescents between the ages of 16 and 20) complete the Patient Health Questionnaire-2 (PHQ-2) to screen for depressive symptoms during each primary care visit. Information on depression is also available via the EHR within each patient's problem list and billing codes. Adolescent patients will be identified who have been seen within an ICCE clinic in the last year with: 1) a score of ≥ 3 on their last PHQ-2 assessment (i.e., the optimal cut-point for identifying those who are symptomatic⁶³), 2) depression listed on their problem list, *or* 3) a depression-related billing code associated with their last visit. We will further narrow this list to only those patients who reported vaping nicotine during their last visit. Patients on the recruitment report will be contacted via the patient EHR portal (MyChart) or e-mail (based on patient preferences in the EHR) by a study team member inviting them to participate in the research study. Within South Carolina, the legal age to consent to medical treatment is 16.

At age 16, all MUSC patients are eligible to receive their own patient portal account and parents/guardians can be appointed as proxies. If participants do not respond to the initial invitation within 72-hours, we will contact them via phone, e-mail, and/or text-message (also based on patient communication preferences within the EHR) to ensure they received the initial study invitation message. If interested, participants will complete an eligibility screening via REDCap to determine study eligibility. After determination of eligibility, a member of the study team will complete remote electronic informed consent (e-consent) with the participant via REDCap⁷⁶. Participants will receive a link to an electronic consent form that they can review and sign. Parents/guardians of participants under 18 years old will participate with the adolescent in the screening, evaluation, and informed consent/assent procedure. Participants 18 years and older will be able to provide their own informed consent. Review of the consent form will be paired with a phone call with an IRB-approved member of the research team to ensure that the consent form is read in full and that all questions are answered prior to trial enrollment. All participants will electronically sign informed consent forms that have been IRB-approved once the study is explained to them in full and they have stated that they understand what is being asked of them. Participants will be given the opportunity to ask questions about their participation throughout the course of the study. Participants will be given a study phone number and e-mail address to contact for questions. Particular caution will be exercised in obtaining informed adolescent assent separately and independently from parental consent to limit potential for coercion. To this end, an initial step in participant recruitment involves obtaining parental/legal guardian permission for participation by the adolescent. Once parental consent is secured, youth will be asked separately and independently for informed consent (i.e., parental consent will not be used to persuade teens to participate). This approach is considered very effective in minimizing coercion to participate. The complex issues of informed consent and assent, and related limitations of confidentiality, as they apply to adolescents and their parents/guardians, are understood by the investigative team and will be communicated clearly during screening and consent. In the case of adolescents in South Carolina Department of Social Services custody, state guidelines regarding consent for clinical research participation will be followed.

Protections Against Risk

The recruitment project is stored in REDCap and only study team members will have access to the recruitment project database. The research team will only have access to the REDCap recruitment project while actively enrolling for the study. The recruitment project will be stored separately from the project containing research data. The recruitment REDCap project will potentially contain both identifiers and health information in the same project. All screening information will be kept in a password protected REDCap database. Only key study personnel will have access to the database. If an individual is not eligible to participate, his/her screener will include his/her first name and last initial and the reason for disqualification. Eligible participants' full name, telephone number and e-mail address will be recorded in the database. This is the only place where participants' names and subject identification numbers appear together. Eligible participants will be assigned a subject number, will complete informed consent (see procedures above), will be randomized (Aim 2), will complete baseline assessments, and subsequently will receive their randomized intervention (or will complete focus group Aim 1).

Upon completing eligibility screening, if study eligible, individuals will be provided with a verbal overview of the study, asked to review a consent form, and asked to provide informed consent (or assent, if under the age of 18). Participants will be informed of limitations of confidentiality (i.e., abuse or neglect, intention to harm self or someone else) both verbally and in writing during the informed consent process. The consent form will include the participant's name, but not his/her subject number. Consent forms will be provided in English. As utilization of VapeX requires that participants are able to read, participants unable to read the consent form on their own will not be included.

Regarding questionnaire data, data will be obtained for research purposes only. All data will be collected, stored, and managed via REDCap, which is a secure, web-based application designed exclusively to support

data capture for research studies. REDCap includes real time validation rules with automated data type and range checks at the time of entry. The underlying database is hosted in a secure data center at MUSC and includes redundancy, failover capability, backups and extensive security checks. The system has several layers of protection including user/group account management, "Data Access Groups" which allow data to be entered by multiple groups in one database with segmented user rights for entered data, audit trails for all changes, queries and reports, and Secure Sockets Layer (SSL) encryption. Name and relevant contact information will be obtained to provide compensation and every effort will be made to maintain subject confidentiality, in accordance with HIPAA. All data will be identified only by code numbers (participant IDs). Participant IDs will be linked to participants' names in a password-protected file that is accessible only to the PI and trained research staff.

Regarding user privacy while using VapeX, users will create a username and password in order to login to their account without storing their true identity. In VapeX, we will store a one-way hashed version of the patient's email address to support password reset and unique identification, but that identification will not be traceable back to the user's true identity. We will not store any personally identifiable information (e.g., first name, last name, email address, phone number) of users in our app database. VapeX will be HIPAA compliant, which we believe will be critical not only for protecting patient information, but also for ensuring that VapeX will be a viable commercial treatment option. We will use a HIPAA-compliant server protected by industry-standard safeguards to prevent unauthorized access. Since we are not associating patient health information with personally identifiable information there will not be a risk of unauthorized release of patient medical data in the event of a security breach. User personal information will be contained behind secured networks and will only be accessible by the investigators, who will have special access rights to such systems. In addition, all sensitive information users supply will be encrypted via Secure Socket Layer (SSL) technology. We will not sell, trade, or otherwise transfer personally identifiable information to outside parties. Our privacy policy will be available within the app for users to view at any time. This plan is consistent with that used by our partnering app development company, MountainPass Technology LLC, in several other previous products with similar protection requirements. [name] from MountainPass has expertise in HIPAA-compliant software development and will oversee all aspects of HIPAA compliance.

Protection against risk resulting from depressive symptoms includes the following: Regarding suicidal ideation and broader mental health concerns, [name] (or back-up clinician), a licensed clinical psychologist, will take appropriate action as outlined by the MUSC IRB, NIH, and the State of South Carolina, which may include paging the participant's referring physician, disclosing information to the participant's parent/legal guardian, contacting the authorities and/or pursuing involuntary commitment at a mental health facility. If participants present no imminent danger but also need more extensive treatment of mental health concerns, they (and their parent/legal guardian, as appropriate) will be given appropriate referrals. As noted above, BDI-II data will be monitored over time in order to detect any possible clinical deterioration. BDI-II data will be monitored using only the participants' subject numbers. Should a participant evidence clinical deterioration, [name] will then use the participant database in order to obtain contact information for the participant based on their subject number. We will also form a Data Safety and Monitoring Board (DSMB) comprised of individuals with expertise in adolescent depression and substance use treatment, primary care, and clinical trials, as well as a statistician. If the percent of serious or severe AEs related to clinical deterioration appears to be greater than 5% the DSMB will be notified to make a decision on early termination of the study.

Regarding recordings, all focus group sessions will be audio recorded and transcribed with recordings stored on an MUSC secure, password protected server. Recordings will be destroyed within one year of recording. Only IRB approved research staff will have access to recordings. Recordings will be destroyed within 12 months of completion of the entire study. Only IRB approved research staff will have access to recordings.

